2. STUDY OBJECTIVES

The primary objectives of this study are to evaluate the effect of NTZ administered orally 600 mg twice daily for 6 weeks in preventing symptomatic laboratory-confirmed COVID-19 and other VRIs in healthcare workers and others at high risk of contracting SARS-CoV-2 infection compared to that of a placebo.

The secondary objectives of this study are to evaluate the effect of NTZ administered orally 600 mg twice daily for 6 weeks in (i) preventing mortality due to COVID-19 or complications thereof, and (ii) reducing the proportion of subjects (with or without symptoms) testing positive for antibodies to SARS-CoV-2 at either of the Week 6 or Week 8 visits.

Exploratory objectives include (i) hospitalization due to VRI or complications thereof, (ii) mortality due to VRI or complications thereof, (iii) proportions of subjects experiencing acute respiratory illness (ARI), (iv) hospitalization due to ARI or complications thereof, and (v) mortality due to ARI or complications thereof.

Other important objectives include evaluation of the safety of NTZ by analysis of adverse events and evaluation of relationships between pharmacokinetics and clinical or virologic responses.

3. STUDY DESIGN

The study will be a multicenter, stratified, randomized, double-blind, placebo-controlled trial to evaluate the efficacy and safety of NTZ for pre- and post-exposure prophylaxis of COVID-19 and other VRIs.

Subjects will be stratified according to their most likely location of exposure, which is a proxy for exposure to SARS-CoV-2 and other VRIs. The strata are:

- Emergency Department
- Intensive Care Unit
- COVID-specific Care Unit
- Walk-in Clinic
- Paramedics and other first responders (e.g., firefighter/EMT)
- Social Activities (3-5 per week)
- Social Activities (>5 per week)

Within strata, subjects will be randomized 1:1 to one of the following groups:

- Group 1 (NTZ): Two NTZ 300 mg tablets b.i.d. for 6 weeks
- Group 2 (Placebo): Two placebo tablets b.i.d. for 6 weeks

This study is expected to run from April 2020 through April 2021.

Rationale for important issues in the study design is described below:

- *Rationale for study design.* *In vitro* data suggest NTZ may be effective against the most common viruses associated with VRIs including SARS-CoV-2. Except for influenza, there are no drugs or vaccines commercially available to prevent VRIs, especially pandemic and outbreak strains of non-influenza viruses like SARS-CoV-2. In the case of influenza these drugs are limited to only the neuraminidase inhibitors for chemoprophylaxis and the vaccine has been demonstrated to be less effective in elderly patients. This study is designed to determine if a drug with broad-spectrum antiviral activity like NTZ can prevent VRIs.
- *Choice of NTZ dose and duration of treatment.* The dose of NTZ was selected based upon safety, tolerability and pharmacokinetics data from prior clinical experience with nitazoxanide. Extended release tablets at a dose of 600 mg administered twice daily with food will be used to achieve and maintain steady state plasma concentrations of tizoxanide above the concentrations required to inhibit respiratory viruses in cell cultures. The tablets will be administered with a B complex vitamin to mask potential chromatemia that may be observed due to the yellow color of nitazoxanide metabolites. A treatment duration of 6 weeks is expected to be sufficient to capture transmission of COVID-19 yet short enough to avoid unnecessary exposure to the medication. Studies of oseltamivir for prophylaxis of influenza have employed a 6-week treatment duration. That treatment duration is supported by safety data from prior studies of NTZ and past experience noting prolonged activity of non-influenza viruses that extended for several months (Monto et al. 1987, Falsey et al. 2008, TAMIFLU® Prescribing Information 2019, NTZ 300 mg Tablets Investigators Brochure).
- *Choice of control groups.* A placebo control is appropriate for the study due to lack of any approved active control.
- *Choice of patient population.* The population to be studied includes healthcare workers and others at high risk of contracting SARS-CoV-2 and other respiratory virus infections. There are no approved antivirals or vaccines for the prevention of non-influenza respiratory viruses, subjects will not be prevented from being prescribed rescue medication for complications if warranted. Therefore, participation in the study will not pose unreasonable risk to any eligible subject. To avoid the potential for sharing medications among subjects in the same household, subjects will be excluded if they reside in a household with a family member currently enrolled as a participant in the study.
- *Choice of Vitamin B Complex Supplement.* All subjects will receive a vitamin B complex supplement ([REDACTED]) one tablet twice a day with study medication. This dose follows the manufacturer's labeled dosing. The purpose of the supplement is to help mask any chromatemia attributed to NTZ and aid in maintaining study blinding. The supplement will supply each subject with the following Percent Daily Values based on a 2,000 calorie diet: vitamin B1 1,333%, vitamin B2 824%, vitamin B3 240%, vitamin B5 360%, vitamin B6 1000%, vitamin B7 100%, vitamin B12 15,000%, folate 100%, and vitamin C 267%. Considering this supplement will provide well beyond the needed

daily allowance of these water-soluble vitamins, excess amounts are expected to be excreted in the urine and provide discoloration.

- *Choice of Patient-Reported Outcome Instrument.* This clinical trial will use the InFLUenza Patient-Reported Outcome Questionnaire (FLU-PRO[®]).

FLU-PRO[®] was developed with the support of the U.S. Department of Health and Human Services through the National Cancer Institute and the National Institutes of Allergy and Infectious Diseases, National Institutes of Health, in response to the need for improved metrics to evaluate treatment effect in clinical trials of drugs for the treatment of influenza and other respiratory tract viral diseases. It was developed and validated in accordance with FDA's guidance, "Patient-Reported Outcome Measures: Use in Medical Product Development to Support Labeling Claims." It has also been validated for use on an electronic device as part of an electronic diary ("eDiary") that can time stamp diary entries to ensure timely recording, thereby mitigating risks of recall bias. We will use an electronic diary for this clinical trial. FLU-PRO[®] was separately validated for use in a population with non-influenza like illness and also has recently been used in vaccine studies with older adults for the prevention of RSV (Powers et al. 2018, Yu et al. 2020).

- *Choice of ARI Definition.* The primary endpoint of this trial requires a determination that an ARI has occurred. We have defined ARI as "≥0.5 increase from baseline in mean symptom score for the chest/respiratory FLU-PRO domain or ≥0.5 increase from baseline in mean symptom score for at least two of the following FLU-PRO[®] domains: body/systemic, nose, throat." In arriving at this definition, we reviewed published mean FLU-PRO[®] symptom score data over the course of RSV illness (Yu et al. 2020) as well as data from recently completed clinical trials in approximately 3,000 subjects with colds and influenza (Romark, data on file). The ARI definition requires an increase in symptom scores from baseline, although the magnitude of the required increase (≥0.5) in mean domain scores is low, and we are requiring that the increase in mean score be achieved for only one or two of the four domains.

4. SUBJECT SELECTION

The criteria for inclusion and exclusion are defined below:

4.1. Inclusion Criteria

1. Males and females at least 18 years of age or of legal consenting age based on local requirements.
2. Persons at increased risk of contracting COVID-19, including:
 - a. Healthcare workers with known direct occupational exposure to COVID-19 within 7 days prior to enrollment. A qualifying person (i) provides healthcare to patients and/or (ii) typically positions themselves within 6 feet of patients ("close contact") and (iii) is a full-time employee (average of ≥ 24 hrs/week) in a high contact area (Emergency Department, Intensive Care Unit, COVID-specific Care Unit, Walk-in Clinic, Paramedic/First Responder).

- b. Persons participating in social activities without the practice of generally accepted social distancing practices at least three times per week. Qualifying activities include the presence of at least 10 people in close (<6 feet) proximity to each other without masks or other personal protective equipment (e.g., socializing at bars or community/social centers, in-home social gatherings, classes or trainings, etc.). These subjects must have engaged in such activities at least three times in the past 7 days and plan to continue these activities during the study.
3. Must have a smartphone, tablet, computer, or other qualifying internet-enabled device and daily internet access.
4. Occupational exposure to a person infected with SAR-CoV-2 within 7 days prior to enrollment or social interaction as defined in criterion 2(b).
5. Willing and able to provide written informed consent and comply with the requirements of the protocol, including completion of the subject diary.

4.2. Exclusion Criteria

1. Subjects not at increased risk of contracting SARS-CoV-2 from occupational or social behaviors.
2. Subjects with known severe heart, lung, neurological or other systemic disease that the Investigator believes could preclude safe participation.
3. Subjects with a history of COVID-19 or known to have developed anti-SARS-CoV-2 antibodies or received a SARS-CoV-2 vaccine.
4. Subjects who experienced a previous episode of acute upper respiratory tract infection, otitis, bronchitis or sinusitis or received antibiotics for these conditions or antiviral therapy for influenza within two weeks prior to and including study day 1.
5. Subjects residing in the same household with another family member currently participating in the study.
6. Receipt of any dose of NTZ within 7 days prior to screening.
7. Treatment with any investigational drug or vaccine therapy within 30 days prior to screening and willing to avoid them during the course of the study.
8. Known sensitivity to NTZ or any of the excipients comprising the study medication.
9. Subjects unable to swallow oral tablets or capsules.
10. Females of childbearing potential who are either pregnant or sexually active without the use of birth control. Female subjects of child-bearing potential that are sexually active must have a negative baseline pregnancy test and must agree to continue an acceptable method of birth control for the duration of the study and for 1 month post-treatment. A double barrier method, oral birth control pills administered for at least 2 monthly cycles prior to study drug administration, an IUD, or medroxyprogesterone acetate administered intramuscularly for a minimum of one month prior to study drug administration are acceptable methods of birth control for inclusion into the study. Female subjects are considered of childbearing potential unless they are postmenopausal (absence of

menstrual bleeding for 1 year - or 6 months if laboratory confirmation of hormonal status), or have had a hysterectomy, bilateral tubular ligation or bilateral oophorectomy.

11. Females who are breastfeeding.
12. Subjects with active respiratory allergies or subjects expected to require anti-allergy medications during the study period for respiratory allergies.
13. Subjects taking medications considered to be major CYP2C8 substrates, refer to [Table 7](#).
14. Subjects who, in the judgment of the Investigator, will be unlikely to comply with the requirements of this protocol including completion of the subject diary.

5. STUDY PROCEDURES

5.1. Screening Evaluation (Day -30 to Day 1)

Before screening, subjects will be informed of the nature of study, and written consent must be obtained prior to participation. After giving informed consent, the subject will be assigned a subject number, and the following procedures will be carried out:

1. Survey of COVID-19 exposure.
2. Complete medical history.
3. Physical examination including body weight and vital signs (blood pressure, pulse, respiratory rate and body temperature).
4. Collection of demographic information and smoking history.
5. Urine pregnancy test for all females of childbearing potential (must be performed Day 1).
6. Evaluation according to eligibility (inclusion and exclusion) criteria.

The information collected during the screening period must be current through the time of randomization.

5.2. Baseline (Day 1, may be same day as screening evaluation)

At baseline, the following procedures will be carried out:

1. Collection of a nasopharyngeal swab sample using a single nylon flocced dry swab inserted into both nostrils for RT-PCR.
2. Collection of blood sample for laboratory safety tests and anti-SARs-CoV-2 antibodies.
3. Collection of a urine sample for routine urinalysis (appearance, glucose, protein and blood).
4. Review and recording of any concomitant medications.
5. Provision of an electronic symptom diary to subject and subject completion of baseline electronic diary under supervision and instruction of study site personnel.

6. Randomization and dispensing of study medication (medication assigned in sequential order).
7. Administration of the first dose of study medication with food (< 1 hour after food intake) and a B complex vitamin ([REDACTED]) under observation of Investigator or a member of Investigator's staff, and entry in the medication administration record.
8. Instruct subject regarding:
 - a. *Administration of study medication.* Subjects will be instructed to take the study medication (two tablets) twice daily with the morning and evening meals, approximately every 12 hours (< 1 hour after food intake, preferably a high-fat meal but at a minimum a cereal bar) and a B complex vitamin ([REDACTED]).
 - b. *Completion of subject diary.* Subjects will be instructed on completion of the electronic diary.
 - c. *Use of birth control.* Female subjects of childbearing potential, if sexually active, will be instructed to continue an acceptable method of birth control for the duration of the study and for 1 month post-treatment. Acceptable methods of birth control include a double barrier method, oral birth control pills, an IUD, or medroxyprogesterone acetate administered intramuscularly.
 - d. *Follow-up visits:* Subjects will be instructed on the study schedule and follow up visits at Week 3, Week 6 and Week 8.
 - e. *Seeking emergency care or contacting the study physician or nurse:* Subjects must be informed to seek emergency medical care or contact the study physician or nurse if they develop any of the following symptoms listed below during the full 8-week study and follow-up period.

CONTACT STUDY PHYSICIAN, IF:

- Trouble breathing including shortness of breath
 - Severe headache, stiff neck, confusion or excessive somnolence
 - If fever ($\geq 99^{\circ}\text{F}$ or $\geq 37.2^{\circ}\text{C}$) returns after being absent for 24 hours
 - Increased difficulty breathing
 - Wheezing develops
 - New pain develops or pain localizes to one area, such as an ear, the throat, the chest, or the sinuses
 - Symptoms become more severe or frequent
 - Symptoms recur or any difficulty breathing following 5-10 days resolution of illness
 - An allergic-like reaction occurs or is suspected
 - Abnormal behavior
- f. *Local public health guidelines:* Subjects will be advised to follow local public health guidelines for SARS-CoV-2 infection control.

5.3. Daily Day 1 through Week 6

Subjects will keep a daily diary to chart study medication and answer the question, “do you feel like you have symptoms of a cold or flu?” If the subject responds “yes”, they will be prompted to complete a full symptom diary questionnaire (FLU-PRO[®]) and contact the Investigator. A study physician, nurse or other designated site personnel will review each subject’s electronic diary entries daily to ensure compliance with collection of diary data. If a subject has not completed his/her diary or if errors are suspected, the study personnel will contact the subject to implement appropriate corrective actions.

If the subject reports (i) at least one of the Lower Respiratory Symptoms presented in [Table 5](#) below or (ii) at least one symptom from each of the Upper Respiratory Symptoms and Systemic Symptoms categories presented in [Table 5](#) below, the subject will then contact the study physician to complete a “Suspected ARI Visit” with the procedures provided below. All subjects meeting this criteria will complete a “Suspected ARI Visit” as soon as possible, but in any event within 5 days of the first diary at which these criteria are met for each episode of suspected ARI regardless of patient or physician assessment of illness nature or severity.

Table 5: Clinical Illness Required for Diagnosis of ARI¹ (adapted from [Yu et al. 2020](#))

Upper Respiratory Symptoms	Lower Respiratory Symptoms	Systemic Symptoms

 • Nasal congestion/rhinorrhea (runny or dripping nose, congested or stuffy nose, head congestion, sinus pressure)² • Sore throat (sore or painful throat)² 	
 • Cough (coughing, chest congestion, chest tightness, dry or hacking cough, wet or loose cough)² • Dyspnea (shortness of breath)² • Sputum (coughing up sputum or phlegm)² • Wheezing 	
 • Myalgias or arthralgias (body aches or pains)² • Fatigue (weak or tired, sleeping more than usual)² • Headache • Decreased appetite (lack of appetite, did not feel like eating)² • Feverishness (felt hot, chills or shivering, felt cold, sweating)²

¹ Suspected ARI requires self-reporting of any Lower Respiratory Symptom, or at least one Upper Respiratory Symptom together with one Systemic Symptom.

² Lay language used in the FLU-PRO[®] questionnaire is presented in parentheses.

5.4. Suspected ARI Visit

Subjects requiring Suspected ARI Visit will be evaluated as follows:

1. Physical examination as warranted by the Investigator for any change from baseline.
2. Body weight and collection of vital signs to include blood pressure, pulse, respiratory rate and body temperature.

3. Collect a nasopharyngeal swab sample using a single nylon flocculated dry swab inserted into both nostrils for RT-PCR at the Suspected ARI Visit, 24 to 36 hours later, and then again 4 to 5 days later.
4. Collect a fecal specimen for RT-PCR at the Suspected ARI Visit, 24 to 36 hours later, and then again 4 to 5 days later.
5. The subject will complete a FLU-PRO[®] symptom diary daily until he/she responds “yes” to the FLU-PRO[®] question, “Have you returned to your usual health?” for 3 consecutive days or until the Week 8 Visit, whichever occurs first. The daily FLU-PRO[®] diary will be completed between 7:00 pm and 11:00 pm.
6. Review and recording of concomitant medications.
7. Review and recording of adverse events/side effects.
8. Laboratory investigations for safety may be performed as warranted based upon the Investigator’s judgment.
9. If a subject tests positive for a respiratory virus by RT-PCR, that subject may receive standard of care as clinically warranted by the Investigator.

Regardless of symptoms or laboratory data, the subject will continue treatment until the 6-week treatment period has ended.

5.5. Week 3 (±7 days) and Week 6 Evaluations (±2 days)

Subjects will attend in-clinic visits at Week 3 and Week 6, and the following procedures will be performed:

1. Physical examination as warranted by the Investigator for any change from baseline.
2. Body weight and collection of vital signs to include blood pressure, pulse, respiratory rate and body temperature.
3. Collection of blood sample for laboratory safety tests, pharmacokinetics (pre-dose, at least six hours after the most recent previous dose) and anti-SARs-CoV-2 antibodies (antibody testing at Week 6 visit only).
4. Collection of urine sample for routine urinalysis.
5. Review of compliance with study medication, collection of medication bottle with any unused medications (Week 6 visit only), and completion of the pill count log form.
6. Review and recording of concomitant medications.
7. Review and recording of adverse events/side effects and complications. Note that all adverse events and complications must be followed until their resolution or stabilization even beyond the 8-week study period.
8. Review of number and type of social activities.
9. Advise subjects to follow local public health guidelines for SARS-CoV-2 infection control.

5.6. Week 8 Evaluation (+7 days)

Subjects will attend in-clinic visits at Week 8 and the following procedures will be performed:

1. Physical examination as warranted by the Investigator for any change from baseline.
2. Collection of blood sample for anti-SARs-CoV-2 antibodies.
3. Review and recording of concomitant medications.
4. Review and recording of adverse events/side effects and complications. Note that all adverse events and complications must be followed until their resolution or stabilization even beyond the 8-week study period.
5. Document any infections diagnosed during the follow-up period.

5.7. Unscheduled Visit

Subjects requiring an unscheduled visit due to worsening symptoms or adverse events will be evaluated at the discretion of the Investigator as is medically warranted. Tests and/ or procedures performed at this visit may include, but are not limited to, the following:

1. Physical examination as warranted by the Investigator for any change from baseline.
2. Body weight and collection of vital signs to include blood pressure, pulse, respiratory rate and body temperature.
3. Collection of a nasopharyngeal swab sample using a single nylon flocced dry swab inserted into both nostrils for RT-PCR.
4. Collection of blood sample for laboratory safety tests.
5. Collection of urine sample for routine urinalysis.
6. Review of compliance with study medication.
7. Review and recording of concomitant medications.
8. Review and recording of adverse events/side effects.

5.8. Study Discontinuation

Rules for discontinuation of a subject or for discontinuing the study are provided in Section 11.2. All subjects discontinued from the study before Week 6 will be evaluated at study discontinuation using the procedures described above for the Week 6 evaluation. Those discontinued after Week 6 will be evaluated as warranted by the Investigator.

5.9. Plan for Laboratory Safety Tests

A central laboratory will be used for laboratory safety testing. Blood tests will include hemoglobin, hematocrit, complete blood count (total and differential), platelet count, random blood sugar, total cholesterol, HDL, LDL, triglycerides, albumin, AST, ALT, GGT, alkaline phosphatase, bilirubin (total/direct), BUN, creatinine, sodium, potassium, chloride. Routine urinalysis will include appearance, glucose, protein, and blood.

5.10. Plan for Virology Testing and Monitoring Resistance

Blood samples collected at Baseline, Week 6 and Week 8 will be tested for anti-SARS-CoV-2 antibodies at a central laboratory using a validated assay (when such become available).

Virology testing of nasopharyngeal swab samples will be conducted as described below.

1. Collection of samples:

Two nasopharyngeal swabs will be collected from each subject at Baseline (Day 1), at each Suspected ARI Visit, 24 to 36 hours after each Suspected ARI Visit, 4 to 5 days after each Suspected ARI Visit, and as warranted by the Investigator.

A fecal specimen will be collected from each subject at each Suspected ARI Visit, 24 to 36 hours after each Suspected ARI Visit, and 4 to 5 days after each Suspected ARI Visit.

2. Testing of biological samples:

Each nasopharyngeal swab sample will be subjected to RT-PCR using the [REDACTED] [REDACTED] to detect influenza A (non-specific as to subtype); influenza A H1, H1N1 (2009), H3 subtypes; influenza B; RSV A and B; parainfluenza 1, 2, 3 and 4; hMPV; adenovirus; human EV/RV; coronavirus NL63, HKU1, 229E and OC43; *Chlamydomphila pneumoniae*; and *Mycoplasma pneumoniae*. The [REDACTED] [REDACTED] will be used to test for SARS-CoV-2.

Each fecal sample will be subjected to RT-PCR using the [REDACTED] [REDACTED] [REDACTED] will be used to test for SARS-CoV-2.

3. Drug susceptibility testing:

If any Suspected ARI Visit nasopharyngeal swab sample is positive for a VRI, the virus will be isolated (if possible) and tested for susceptibility to tizoxanide.

4. Storage of samples: All samples collected during the study will be stored for at least 2 years for potential future testing.

5. Clinical virology laboratory for diagnostic testing:

[REDACTED]
[REDACTED]
[REDACTED]

6. Clinical virology laboratory for drug susceptibility testing:

[REDACTED]
[REDACTED]
[REDACTED]

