Primary Efficacy Parameters:	
The proportion of subjects with symptomatic laboratory-confirmed COVID-19 identified after start of treatment and before the end of the 6-week treatment period.The proportion of subjects with symptomatic laboratory-confirmed VRI identified after the start of treatment and before the end of the 6-week treatment period

- Secondary Efficacy Parameters:**
- i. Mortality due to COVID-19 or complications thereof.
 - ii. The proportion of subjects (with or without symptoms) testing positive for antibodies to SARS-CoV-2 at either of the Week 6 or Week 8 visits.
- Exploratory Efficacy Parameters:** Proportion of subjects hospitalized due to viral respiratory illness (VRI) or complications thereof; mortality due to VRI or complications thereof; proportion of subjects experiencing acute respiratory illness (ARI); proportion of subjects hospitalized due to ARI or complications thereof; mortality due to ARI or complications thereof.
- Safety Parameters:** Adverse events
- Biological Samples:** Blood and urine samples for safety will be collected for all subjects at baseline, Week 3 and Week 6. Blood samples for pharmacokinetics will be collected at the Week 3 and Week 6 visits. Blood tests for anti-SARS-CoV-2 antibodies will be collected at Baseline, Week 6 and Week 8. Nasopharyngeal swabs will be collected at baseline for all subjects. Additional nasopharyngeal swabs and fecal specimens will be collected by the Investigator at visits for COVID-19/VRI symptoms.
- Study Centers:** Multicenter, USA
- Trial Duration:** April 2020 – April 2021

Table 1: List of Abbreviations

Abbreviation	Term
AE	Adverse Event
ALT	Alanine Aminotransferase
ARI	Acute Respiratory Illness
AST	Aspartate Aminotransferase
ATP	Adenosine Triphosphate
b.i.d.	Twice Daily
BUN	Blood Urea Nitrogen
CMH	Cochran-Mantel-Haenszel
COPD	Chronic Obstructive Pulmonary Disease
COVID-19	Coronavirus Disease 2019 (caused by SARS-CoV-2)
CRF	Case Report Form
EC50	50% Effective Concentration
EDC	Electronic Data Collection
EV/RV	Rhinovirus/Enteroviruses
FDA	Food and Drug Administration
FLU-PRO	InFLUenza Patient-Reported Outcome Questionnaire
GCP	Good Clinical Practice
GGT	Gamma Glutamyl Transferase
HDL	High Density Lipoprotein
HIV	Human Immunodeficiency Virus
hMPV	Human Metapneumovirus
IC50	50% Inhibitory Concentration
ICF	Informed Consent Form
ICH	International Council for Harmonisation
IDMC	Independent Data Monitoring Committee
IL	Interleukin

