8.3. Response Definitions

ARI:	≥ 0.5 increase from baseline in mean symptom score for the chest/respiratory FLU-PRO domain or ≥ 0.5 increase from baseline in mean symptom score for at least two of the following FLU-PRO [®] domains: body/systemic, nose, throat.
COVID-19:	ARI after start of treatment and before the end of the 6-week treatment period associated with detection of SARS-CoV-2 by RT-PCR assay of nasopharyngeal swab.
VRI:	ARI after start of treatment and before the end of the 6-week treatment period associated with detection of any respiratory virus by RT-PCR assay of nasopharyngeal swab.

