8.4.1. Efficacy Analyses

Efficacy analyses will be based on a population consisting of all subjects randomized without a laboratory-detected viral respiratory infection at the baseline visit (intention-

to-treat or ITT population). All chi-square analyses will be calculated with appropriate continuity corrections.

There will be two primary efficacy analyses:

- The proportion of subjects experiencing COVID-19 in the NTZ treatment group will be compared to that of the placebo treatment group using a two-sided Cochran-Mantel-Haenszel (CMH) chi-square test ($\alpha = 0.049$).
- The proportion of subjects experiencing VRI in the NTZ treatment group will be compared to that of the placebo treatment group using a two-sided CMH chi-square test ($\alpha = 0.001$).

Secondary analyses will be performed as follows:

- The proportion of subjects experiencing COVID-19 or VRI for treatment vs control will be tested within strata using Pearson chi-square tests at an unadjusted $\alpha = 0.05$.
- Confidence intervals (95% confidence level) will be produced for the overall odds ratio and for the odds ratios for NTZ vs placebo for each stratum.
- Proportions of subjects experiencing mortality due to COVID-19 or complications thereof will be compared by treatment group using a two-sided Pearson chi-square test (unadjusted $\alpha = 0.05$).
- Proportions of subjects (with or without symptoms) testing positive for antibodies to SARS-CoV-2 at either of the Week 6 or Week 8 visits will be compared by treatment group using a two-sided Pearson chi-square test (unadjusted $\alpha = 0.05$).

Exploratory analyses will be performed as follows:

- Proportions of subjects experiencing each of the following will be compared by treatment group using a two-sided Pearson chi-square test (unadjusted $\alpha = 0.05$): (i) hospitalization due to VRI or complications thereof, (ii) mortality due to VRI or complications thereof, (iii) proportions of subjects experiencing acute respiratory illness (ARI), (vi) hospitalization due to ARI or complications thereof, (v) mortality due to ARI or complications thereof.

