2.2 Analysis Populations

2.2.1 Population Definitions

Subjects will be considered enrolled in the study upon completion of the baseline procedures. The following analysis populations will be used in the study.

- **Safety Population** – the safety population includes all patients who are enrolled in the study and that have received at least one dose of the assigned treatment arm (NTZ or placebo).
- **Intention-to-Treat Population (ITT)** – the ITT population includes all patients in the safety population who did not have a laboratory detected respiratory virus infection at the baseline visit.

The safety population will be used for all safety analyses. The ITT population will be the primary population for all efficacy analyses.

A data listing displaying the patients excluded from the ITT population will be created, as shown in the Table Requirements Document. This listing will be relative to all patients in the safety population.

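### Any respiratory virus on the Day 1 swab removes a subject from the COVID-19 analyses as well as the VRI analysis; for the COVID-19 endpoints only a Day 1 SARS-CoV-2 positive needs to be excluded

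*Protocol*

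**What the plan says.** The Day 1 swab is taken from everyone: "Nasopharyngeal swabs will be collected at baseline for all subjects" (Protocol synopsis). Protocol 5.10 sends each swab through a multi-virus RT-PCR panel and a separate SARS-CoV-2 assay. Besides influenza and RSV, the panel covers "parainfluenza 1, 2, 3 and 4; hMPV; adenovirus; human EV/RV; coronavirus NL63, HKU1, 229E and OC43".

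The rule itself is in the analysis sections. Protocol 8.4.1 bases efficacy on "all subjects randomized without a laboratory-detected viral respiratory infection at the baseline visit". SAP 2.2.1 takes treated subjects "who did not have a laboratory detected respiratory virus infection at the baseline visit" and adds: "The ITT population will be the primary population for all efficacy analyses". Neither document limits the exclusion by virus or by endpoint. The table list in SAP Section 8 puts COVID-19, COVID-19 mortality and antibody status all on this ITT set.

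The COVID-19 endpoint is virus-specific: an ARI "associated with detection of SARS-CoV-2 by RT-PCR assay of nasopharyngeal swab" (Protocol 8.3; SAP 4.1 agrees). The VRI endpoint accepts any respiratory virus.

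A positive Day 1 swab is not among the exclusion criteria in Protocol 4.2, so these subjects are randomised, dosed and followed.

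**The concern.** One filter serves two endpoints that need different ones. For VRI, a rhinovirus present on Day 1 could be detected again two weeks later and counted as a new illness, so removing carriers is sensible. For COVID-19, a Day 1 rhinovirus cannot later be read as SARS-CoV-2. That subject is as much in the trial as anyone else, yet a later SARS-CoV-2-positive ARI would not enter the primary test. The same subject is lost from the antibody and COVID-19 mortality comparisons.

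Nothing in the plan restores these subjects. The sensitivity analyses in SAP 2.3 and 4.2.1 deal only with missing endpoints, and no efficacy analysis is planned in all randomised or all treated subjects. The sample size sections (Protocol 8.1, SAP 1.3) make no allowance for the loss. In a trial sized on 24 COVID-19 cases, each case left out matters. The result also stops applying to people who carry another virus when they start prophylaxis.

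**Working it through.** **Size of the panel.** Counting influenza A once: influenza A 1 + influenza B 1 + RSV 2 + parainfluenza 4 + hMPV 1 + adenovirus 1 + EV/RV 1 + seasonal coronaviruses 4 = 15 viruses besides SARS-CoV-2. Listing the three influenza A subtypes separately gives 18. The two bacteria on the panel do not trigger the rule.

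**Inputs.** COVID-19 rate 1% over six weeks, used as the placebo rate; 80% reduction, so 0.2% on NTZ; expected N 2,842; about 4,000 for 90% power; target 24 cases (Protocol 8.1, SAP 1.3). Alpha 0.049 two-sided with continuity correction (SAP 4.2.1). Cap 4,000 (Protocol synopsis).

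**Reproducing the plan's figures.**

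- Normal approximation: power = Φ{[|p0 − p1| − z√(2p̄(1 − p̄)/n)] / √[(p0(1 − p0) + p1(1 − p1))/n]}. With n = 1,421 per arm, p̄ = 0.006 and z = 1.969, this is Φ{(0.0080 − 0.0057)/0.0029} = 78.6%, against the stated 80.6%.
- The same method needs 3,934 subjects for 90% power, against about 4,000.
- Schoenfeld: 4(1.969 + 1.282)²/(ln 0.2)² = 16.3, so 17 events as stated. Both documents print a hazard ratio of 0.8 there, but 17 events corresponds to 0.2, the 80% reduction. That is a separate matter.
- A simulated seven-stratum CMH test at 2,842 gives about 82.7% without and 74.5% with continuity correction.

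The 74.5% starting value below therefore comes from the planned continuity correction, not from the exclusion.

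**Effect of the exclusion at a fixed sample size.** The documents give no carriage rate. I assume that a share q of 2% to 10% carry only another virus and have the same COVID-19 risk as the rest. Power is exact: two binomials with n(1 − q) per arm, rejecting when the continuity-corrected Mantel-Haenszel chi-square (single stratum) exceeds the 0.049 critical value, 3.875. The larger case uses 2,002 per arm, which divides evenly into seven strata.

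| q | Power near 4,000 | Expected events (pooled rate 0.6%) | Power at 2,842 |
|---|---|---|---|
| 0% | 89.9% | 24.0 | 74.5% |
| 2% | 89.2% | 23.5 | 73.5% |
| 5% | 88.0% | 22.8 | 71.8% |
| 10% | 85.8% | 21.6 | 68.9% |

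The loss is 0.7 to 4.0 points near 4,000 and 1.0 to 5.6 points at 2,842.

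**Effect if enrolment continues to 24 cases within the efficacy population.** Conditional on 24 events, the NTZ share is 0.2/(0.2 + 1.0) = 1/6. The continuity-corrected test rejects in favour of NTZ with 6 or fewer NTZ cases, which has probability 90.9% whatever q is. The cost is then enrolment:

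- At the pooled planning rate of 0.6%, 24/0.006 = 4,000 analysable subjects are needed. That is 4,000/0.98 = 4,082 to 4,000/0.90 = 4,445 randomised, above the cap.
- At the blinded pooled rate of 1.2% quoted in SAP 1.3, 24/0.012 = 2,000 are needed, or 2,000/0.90 = 2,223 with 10% excluded, well below the cap.

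The documents do not say whether the 24 cases are counted in the efficacy population or in all randomised subjects. If in all randomised, 24 × (1 − q) = 23.5 to 21.6 reach the primary test.

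**The case against.** **The filter has a purpose for COVID-19 too.** COVID-19 here is an ARI plus SARS-CoV-2 detection, and ARI is a rise from baseline in FLU-PRO scores. A Day 1 carrier of another virus may start with raised scores, or may supply the ARI from that virus while SARS-CoV-2 is found incidentally. Protocol 1.2.1 describes NTZ as active against several of these viruses, so treatment could change the symptom component without preventing COVID-19. This is a fair argument, but a weak one. The endpoint still requires both a rise from baseline and SARS-CoV-2, and the definition does not disqualify a case in which another virus is also detected after Day 1. The argument cannot apply to antibodies, which need no symptoms.

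**Few subjects are affected.** Exclusion criterion 4 removes anyone with a recent acute upper respiratory infection, up to and including Day 1, which probably lowers carriage. This stands: near 2% carriage the loss is about one point or less.

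**The cases are not hidden.** SAP Section 8 lists COVID-19 and antibody status for the safety population and lists the excluded subjects. That is true, but a listing is not an analysis.

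**Stronger readings a reader might infer.** The ITT label invites the inference that dropping randomised subjects biases the comparison. The documents do not support that: in Protocol 5.2 the swab is step 1 and randomisation step 6, and Protocol Section 6 masks laboratory personnel. Nor can the power losses be read as certain, since they rest on an assumed carriage rate and a fixed sample size.

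**Conclusion.** The any-virus exclusion fits VRI and is needlessly wide for the COVID-19 primary, COVID-19 mortality and antibody analyses. It does not bias the comparison of arms; it costs events, precision and generalisability.

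The size depends on two things the documents leave open: the carriage rate, and the population in which the 24 cases are counted. With 2% to 10% carriage and a fixed sample size, power falls from 89.9% to between 89.2% and 85.8% near 4,000 subjects, and from 74.5% to between 73.5% and 68.9% at 2,842. If cases accrue to 24 in the efficacy population without reaching the cap, power stays near 91% and the price is additional subjects. This is a modest, avoidable inefficiency, worth correcting because the correction is cheap.

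**What to change.** In Protocol 8.4.1 and SAP 2.2.1, define the efficacy population by endpoint:

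- For COVID-19 (primary, COVID-19 mortality, antibodies), exclude only subjects with SARS-CoV-2 detected on the Day 1 swab.
- For VRI, keep the exclusion of subjects with any respiratory virus on that swab.
- Report both denominators in the efficacy tables.
- Repeat the COVID-19 analysis in the any-virus-free set as a sensitivity analysis.
- State in which population the 24 cases are counted.

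SAP version 1.3 is dated 26 April 2024, the protocol expected the trial to run to April 2021, and the documents do not say whether data are unblinded. If they are, keep the primary population as written and present the SARS-CoV-2-only population as a labelled supplementary analysis.

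No new data or subjects are needed. There are two downsides. Two denominators must be reported. SAP 4.1 also defines VRI as including COVID-19, so a COVID-19 case in a Day 1 carrier of another virus would count for COVID-19 but not for VRI. The two primary endpoints would no longer nest exactly, and a table footnote should say so.
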